17.3.2 Sensitivity analyses primary estimand

Any marked difference between the primary statistical analysis and sensitivity analyses will be commented upon in the CTR.

MMRM - retrieved data

A mixed model for repeated measurement (MMRM) with an unstructured covariance matrix will be applied for the statistical analysis. The MMRM model accounts for missing data by an assumption of missingness at random. That is, the trajectory of treatment discontinued subjects is assumed to be as for those subjects on similar treatment that complete treatment. All observed and retrieved (V32A) data will be included in the analysis. Thus this model operates under a different assumption on missingness and includes more observed data. The latter implies that any treatment effect up until premature discontinuation is taken into account.

The MMRM model will include treatment, pre-trial OAD, region and visit as fixed factors and the corresponding baseline value as a covariate. Interactions between visit and all factors and the covariate are also to be included in the model. This model will be referred to as the standard MMRM model

Multiple imputation – copy reference– retrieved data – NI penalty

In this analysis withdrawn and prematurely discontinued subjects from the investigational treatment (IDegLira) arm not having a week 26 measurement are assumed to respond as if treated with a treatment inferior to comparator (IGlar) or any other treatment received after premature treatment discontinuation from the time of treatment discontinuation.

The analysis is similar to the primary analysis except that observed values for prematurely discontinued IDegLira subjects are not set missing (step 1 is left out). Observe that for IDegLira now only missing data after premature discontinuation are imputed by the sequential ANOVAs (step 3 to 5) and this principle is named copy reference (CR); intermittent missing data are imputed by MCMC (step 2). Thus this analysis is to include more observed values and applying the sequential ANOVAs at a later point in the visit structure. The latter implies that any treatment effect up until premature discontinuation is taken into account.

EudraCT No.: 2015-001596-48

CONFIDENTIAL

Date: Version: Status: Page:

20 November 2015 | Novo Nordisk 2.0 Final 76 of 107

Multiple imputation – jump to reference – retrieved data – NI penalty – tipping point

A tipping point analysis will be performed based on the model of the primary analysis. Subjects who prematurely discontinue from the IDegLira arm are assumed to have received a treatment inferior to IGlar or any other treatment received after premature treatment discontinuation. The extent of the inferiority (also termed the 'penalty') will be gradually increased to evaluate at which point (penalty) IDegLira is no longer non-inferior to IGlar.

Multiple imputation – jump to reference – retrieved data – NI penalty – CAS

This is a repeat of the primary analysis restricted to the CAS.

Multiple imputation – jump to reference – retrieved data – NI penalty – PP

This is a repeat of the primary analysis restricted to the PP analysis set.

17.3.3 Primary statistical analysis secondary estimand

MMRM

The secondary estimand for the primary objective is difference in change from baseline in HbA_{1c} after 26 weeks between T2DM subjects randomised to IDegLira and IGlar, both in combination with SGLT2i ± OAD, attributable to randomised treatment, if all randomised subjects had tolerated and adhered to treatment until week 26.

This analysis is a repeat of the standard MMRM this time leaving out retrieved (V32A) data.

17.3.4 Sensitivity analyses secondary estimand

ANOVA – LOCF imputation

This analysis is an ANOVA with treatment, pre-trial OAD and region as factors and baseline value as covariate based on the FAS and with missing data imputed by LOCF.

17.4 **Secondary endpoints**

17.4.1 **Confirmatory secondary endpoints**

The confirmatory secondary endpoints of the trial are tested for superiority of IDegLira to IGlar.

Protocol		Date:	20 November 2015	Novo Nordisk
Trial ID: NN9068-4229	CONFIDENTIAL	Version:	2.0	
UTN: U1111-1168-9343		Status:	Final	
EudraCT No.: 2015-001596-48		Page:	77 of 107	

In order to control the overall Type I error, a hierarchical testing procedure will be used. If non-inferiority in glycaemic control (change from baseline in HbA_{1c}) is concluded in the primary statistical analysis of the primary estimand, testing proceeds down the following hierarchy as long as superiority at a given stage is confirmed based on the primary statistical analysis of the primary estimand:

- 1. Superiority in weight change
- 2. Superiority in number of treatment-emergent (severe or BG confirmed symptomatic) hypoglycaemic episodes
- 3. Superiority in glycaemic control (change from baseline in HbA_{1c})
- 4. Superiority in insulin dose (total daily dose [U])

The following paragraphs detail the hypotheses and statistical analyses of the confirmatory secondary endpoints.

17.4.1.1 Primary statistical analyses primary estimand

Body weight

Let D_W be the mean treatment difference (IDegLira – IGlar) in change from baseline in body weight. The null-hypothesis of IDegLira not superior will be tested against the alternative hypothesis of superiority as given by

$$H_0$$
: $D_W \ge 0$ kg against H_A : $D_W < 0$ kg.

Superiority will be considered confirmed if the test procedure was not stopped and if the upper bound of the two-sided 95% confidence interval for D_W (mean treatment difference in change from baseline in weight) is strictly below 0 kg. This is equivalent to using a one-sided test of size 2.5%, i.e. the Type I error rate is controlled at 2.5% one-sided. The change from baseline in body weight after 26 weeks will be analysed with the J2R pattern mixture model for HbA_{1c} , substituting body weight for HbA_{1c} and leaving out the non-inferiority penalty (step 6).

Treatment-emergent hypoglycaemic episodes

Let RR be the rate ratio (IDegLira/IGlar) of the rate of treatment-emergent severe or BG confirmed symptomatic hypoglycaemic episodes during 26 weeks. The null-hypothesis of IDegLira not superior will be tested against the alternative hypothesis of superiority as given by

$$H_0$$
: $RR \ge 1$ against H_A : $RR < 1$.

Superiority will be considered confirmed if the test procedure was not stopped and if the upper bound of the two-sided 95% confidence interval for RR (rate ratio of rate of treatment-emergent severe or BG confirmed symptomatic hypoglycaemic episodes during-treatment) is strictly below 1. This is equivalent to using a one-sided test of size 2.5%, i.e. the Type I error rate is controlled at

Protocol		Date:	20 November 2015	Novo Nordisk
Trial ID: NN9068-4229		Version:	2.0	
UTN: U1111-1168-9343	CONFIDENTIAL	Status:	Final	
EudraCT No.: 2015-001596-48		Page:	78 of 107	

2.5% one-sided. The number of hypoglycaemic episodes will be analysed using a multiple imputation technique for count data under the J2R principle as follows.

For prematurely discontinued subjects the number of events in the missing period (time of premature discontinuation to planned TE period [max of 27 weeks and longest TE exposure time observed in the trial]) will be imputed using a multiple imputation technique³⁸, and assuming that all subjects have an event rate in the period before and after premature discontinuation corresponding to the event rate in the control group (IGlar). This will be done as follows:

- As a first step, a Bayes negative binomial model is fitted to the event rate data to obtain the posterior distribution of model parameters
- In the second step, based on the estimated parameters for comparator (IGlar) in this model, the number of events in the missing period is imputed for all prematurely discontinued subjects. I.e. pre and post discontinuation event rates in the conditional distribution used for imputation are as for comparator (IGlar). Multiple copies (1000 copies) of a complete data set are generated by sampling from the estimated distribution
- In the third step, for each of the complete data sets, the number of events is analysed using a negative binomial model
- In the fourth step, the estimates and standard deviations for the 1000 data sets are pooled to one estimate and associated standard deviation using Rubin's rule³⁷. From these pooled estimates the confidence interval for the treatment ratio and the associated p-value are calculated

The negative binomial model will have a log-link function, and the logarithm of the time period, in which a hypoglycaemic episode is considered treatment-emergent, will be used as offset. The model will include treatment, pre-trial OAD and region as factors.

Glycaemic control

As above, let D be the mean treatment difference (IDegLira – IGlar) in change from baseline in HbA_{1c} . The null-hypothesis of IDegLira not superior will be tested against the alternative hypothesis of superiority as given by

$$H_0: D \ge 0\%$$
 against $H_A: D < 0\%$.

Superiority will be considered confirmed if the test procedure was not stopped and if the upper bound of the two-sided 95% confidence interval for D (mean treatment difference in change from baseline in HbA_{1c}) is strictly below 0%. This is equivalent to using a one-sided test of size 2.5%, i.e. the Type I error rate is controlled at 2.5% one-sided. The change from baseline in HbA_{1c} after 26 weeks will be analysed with the J2R pattern mixture model for HbA_{1c} but leaving out the non-inferiority penalty (step 6).

CONFIDENTIAL

Date: Version: Status: Page:

20 November 2015 | Novo Nordisk 2.0 Final 79 of 107

Insulin dose

Let D_D be the mean treatment difference (IDegLira – IGlar) in insulin dose after 26 weeks. The null-hypothesis of IDegLira not superior will be tested against the alternative hypothesis of superiority as given by

$$H_0: D_D \ge 0 U$$
 against $H_A: D_D < 0 U$.

Superiority will be considered confirmed if the test procedure was not stopped and if the upper bound of the two-sided 95% confidence interval for D_D (mean treatment difference in insulin dose after 26 weeks) is strictly below 0 U. This is equivalent to using a one-sided test of size 2.5%, i.e. the Type I error rate is controlled at 2.5% one-sided. The insulin dose after 26 weeks will be analysed with the J2R pattern mixture model for HbA_{1c}, substituting insulin dose for HbA_{1c}, leaving out the non-inferiority penalty (step 6) and using baseline HbA_{1c} as covariate as there is no baseline dose. That is, in the sequential ANOVAs (step 3 to 5) both insulin dose at previous visits and baseline HbA_{1c} will be included as covariates whilst in the EOT ANOVA (step 7) only baseline HbA_{1c} will be included as covariate.

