Appropriate measures, including encryption of data files containing person identifiable data, will be used to ensure confidentiality of subject data, when they are transmitted over open networks.

Data from central laboratories will be transferred electronically. In cases where data is transferred via non-secure electronic networks, data will be encrypted during transfer.

The subject and any biological material obtained from the subject will be identified by subject number and trial ID. Appropriate measures such as encryption or leaving out certain identifiers will be enforced to protect the identity of subjects in all presentations and publications as required by local, regional and national requirements.

16 Computerised systems

Novo Nordisk will capture and process clinical data using computerised systems that are described in Novo Nordisk Standard Operating Procedures and IT architecture documentation. The use and control of these systems are documented.

Investigators working on the trial may use their own electronic systems to capture source data.

Protocol Trial ID: NN9068-4229 UTN: U1111-1168-9343

EudraCT No.: 2015-001596-48

CONFIDENTIAL

Date: Version: Status: Page:

20 November 2015 | Novo Nordisk 2.0 Final 69 of 107

17 Statistical considerations

Novo Nordisk will analyse and report data from all sites together.

All efficacy endpoints and PRO endpoints will be summarised using the full analysis set (FAS) and safety endpoints will be summarised using the safety analysis set (SAS).

All statistical analyses of efficacy and safety endpoints will be based on the full analysis set (FAS) unless otherwise specified. Confirmatory analyses will include on-treatment data and available retrieved (V32A) data.

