(V32A) from subjects prematurely discontinued from randomised treatment. To estimate this estimand for evaluation of non-inferiority of HbA_{1c}, a pattern mixture model approach³⁵ will be adopted. It mimics an ITT scenario where withdrawn and prematurely discontinued subjects from the investigational treatment (IDegLira) arm not having a week 26 measurement are assumed to be switched to a treatment inferior to comparator (IGlar) or any other treatment received after premature treatment discontinuation. This corresponds to a jump to reference (J2R) principle where a penalty in terms of the NI margin is added to withdrawn or prematurely discontinued subjects in the IDegLira arm. Observe that the J2R principle and use of retrieved (V32A) data in analyses will equalise treatment effects and in turn assay sensitivity in the non-inferiority setting may be jeopardized. The penalty of the non-inferiority margin³⁶ is to remedy this. Multiple copies (1000 copies) of the full dataset will be generated by imputing missing values based on estimated parameters for a subgroup of subjects in the trial. This will be done as follows:

- As a first step, all post-randomisation HbA_{1c} values for prematurely discontinued subjects in the investigational treatment group (IDegLira) not having retrieved (V32A) data are set to missing
- In the second step, intermittent missing values are imputed using a Markov Chain Monte Carlo (MCMC) method, in order to obtain a monotone missing data pattern. This imputation is done for each treatment group separately and 1000 copies of the dataset will be generated. Subjects from either group with retrieved (V32A) data will now have a non-missing data pattern
- In the third step, for each of the 1000 copies of the dataset, an ANOVA model with pre-trial OAD and region as factors, and baseline HbA_{1c} as covariate is fitted to the change in HbA_{1c} from baseline to first planned HbA_{1c} measurement visit after randomisation (V10) based on the control group (IGlar) and subjects with retrieved (V32A) data in the investigational group (IDegLira). The estimated parameters, and their variances, from this model are used to impute missing values at the first planned HbA_{1c} measurement visit after randomisation (V10) for subjects in both treatment groups, based on their pre-trial OAD, region and HbA_{1c} at baseline

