2.16 Section 12.2 Reporting of adverse events

All events meeting the definition of an AE must be collected and reported. This includes events from the first trial-related activity after the subject has signed the informed consent until the end of the two post-treatment follow-up periods. Please be aware that hypoglycaemic episodes should not be reported before any trial drug is given e.g. hypoglycaemic episodes should be reported from the randomisation visit (V2). Subjects discontinuing trial product prematurely (see section 6.4) will be contacted every 4th week and asked for information about antidiabetic medication, MACE and SAEs. These subjects should finally come in for a V32A at week 26, only to assess antidiabetic medication, MACE, SAEs, fasting body weight and a blood sample to measure HbA_{1c}.

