2.22 Section 17.4.1.2 Sensitivity analyses primary estimand

Continuous endpoints, body weight, HbA_{1c} and insulin dose – multiple imputation – conditional copy reference retrieved data

These analyses are repeats of the primary analyses using the *conditional approach* CR principle in place of the *unconditional approach* J2R principle, just as for the *conditional* CR sensitivity analysis of the primary estimand of the primary objective.

Continuous endpoints body weight, HbA_{1c} and insulin dose – multiple imputation – unconditional jump to reference retrieved data - tipping point

Count endpoint hypoglycaemic episodes – multiple imputation – method 2 copy reference

This is a repeat of the primary analysis using the CR principle in place of the J2R principle. More specifically, in In this analysis IDegLira subjects are assumed to have the event rate of the IDegLira arm prior to premature discontinuation and the event rate of IGlar after premature discontinuation. The method follows method 1 the multiple imputation J2R for count data above, but in the second step pre discontinuation rates are the respective groups rates whilst post discontinuation rate is the rate of comparator (IGlar).

Count endpoint hypoglycaemic episodes – multiple imputation – method 1 jump to reference tipping point

This is a repeat of *method 1*the multiple imputation J2R above, now varying a penalty on the post discontinuation event rate until IDegLira is no longer superior to IGlar.

CONFIDENTIAL

Date: Version: Status: Page:

28 November 2016 | Novo Nordisk Final 17 of 19

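### Does the primary hypoglycaemia analysis credit IDegLira discontinuers with on-drug benefit in a way that calls for a change?

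*Protocol*

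**What the plan says.** Section 17.4.1.1 imputes episodes between premature discontinuation and the end of the planned treatment-emergent period. It assumes that "all subjects have an event rate in the period before and after premature discontinuation corresponding to the event rate in the control group", and its second step repeats this: "pre and post discontinuation event rates in the conditional distribution used for imputation are as for comparator (IGlar"). Amendment 2 (2.21) calls this method 1. The sensitivity analysis, method 2 (Amendment 2, 2.22), changes one input: "pre discontinuation rates are the respective groups rates whilst post discontinuation rate is the rate of comparator (IGlar"). A tipping-point analysis repeats method 1, "now varying a penalty on the post discontinuation event rate until IDegLira is no longer superior to IGlar".

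For HbA1c, and by extension body weight and insulin dose, step 1 of the primary analysis in 17.3.1 says that "values for prematurely discontinued subjects in the investigational treatment group (IDegLira) not having retrieved (V32A) data are set to missing". The sensitivity analysis in 17.3.2 leaves that step out, and the protocol states the consequence: "The latter implies that any treatment effect up until premature discontinuation is taken into account".

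The opening of Section 17 says: "Confirmatory analyses will include on-treatment data and available retrieved (V32A) data". The week 26 visit for discontinued subjects is, under Amendment 2 (2.16), "only to assess antidiabetic medication, MACE, SAEs, fasting body weight and a blood sample to measure" HbA1c. It collects no hypoglycaemic episodes, and Section 8.5.2 limits episode reporting to V2 through V33.

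**The concern.** In a negative binomial model, conditioning on the on-drug count while assuming the IGlar rate for that period carries any on-drug advantage of IDegLira forward. A low count is read as low personal risk and projected past discontinuation. For weight, HbA1c and insulin dose, the primary analysis removes the on-drug history of IDegLira discontinuers without V32A data, and the version that keeps it is only the sensitivity analysis. For this one endpoint the roles look reversed, and the text neither says so nor gives a reason.

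Hypoglycaemia is the second test in the hierarchy of 17.4.1, with stated power of only about 60%, so a more favourable rule could matter. The tipping point also starts from method 1. A reader who took zero penalty to mean parity with IGlar would overstate robustness. Finally, the general sentence on V32A data appears to promise something that cannot exist for this endpoint.

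**Working it through.** **Inputs.** From Section 17.1: 208 subjects per arm, 15% discontinuing, 1.8 episodes per patient-year (arm not stated), rate ratio 0.66, power of about 60%. From 17.4.1.1: an imputation period of at least 27 weeks. Assumed, because the protocol gives no dispersion k: the value that returns 60% power. Rates are taken as constant, with 52.18 weeks per year.

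**Stated power.** The variance of the log rate ratio is [1/(m₁t) + 1/(m₀t) + 2k]/208, with t = 26/52.18 = 0.498, m₁ the IDegLira rate and m₀ the IGlar rate.
- If 1.8 is the IGlar rate (m₁ = 1.188), k = 2.27: (1.689 + 1.115 + 4.54)/208 = 0.0353, SE 0.188. Then 0.4155/0.188 − 1.96 = 0.25, so power is 60%.
- If 1.8 is the IDegLira rate (m₀ = 2.73), k = 2.74: (1.115 + 0.736 + 5.48)/208 = 0.0352, and power is again 60%.
- With k = 0 the power would be 95% or 99%, so the 60% implies substantial overdispersion.

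**Imputed rate.** For on-drug time t₁ with y₁ episodes, the imputed rate is m₀ × (1/k + y₁)/(1/k + m_pre·t₁). Method 1 sets m_pre = m₀; method 2 sets it to the subject's own arm. For IDegLira discontinuers who ran at their arm's average rate, the mean relative to IGlar is:
- method 1: (1 + k·m₁·t₁)/(1 + k·m₀·t₁), below 1 when the rate ratio is below 1;
- method 2: exactly 1.

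Worked case, k = 2.27, week 13, t₁ = 0.249: (1 + 0.672)/(1 + 1.018) = 0.828.

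| Stop at week | 4 | 8 | 13 | 20 |
|---|---|---|---|---|
| Method 1, k = 2.27 | 0.919 | 0.869 | 0.828 | 0.792 |
| Method 1, k = 2.74 | 0.876 | 0.818 | 0.779 | 0.748 |

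**Overall rate ratio.** With 15% stopping at week 13 and k = 2.27:
- method 1: 0.85 × 0.66 + 0.15 × (13/27 × 0.66 + 14/27 × 0.828) = 0.673;
- method 2: the same with 1 in place of 0.828, giving 0.686.

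With stopping spread uniformly over weeks 0.5 to 26, method 1 gives 0.673 to 0.676 and method 2 gives 0.686. At 25% discontinuation the figures are 0.681 to 0.687 and 0.703.

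**Power and size.** Simulation used 208 per arm, a treatment-only negative binomial model, 20 imputations pooled by Rubin's rule, and 4,000 trials per setting.
- At 15% discontinuation, success is 55 to 56% under method 1 and 51% under method 2. At 25% it is 47 to 50% and 41%.
- At a true rate ratio of 1, one-sided size over both discontinuation levels is 1.4 to 2.3% under method 1 and 0.8 to 1.7% under method 2. When the arms' rates are equal, the two methods use the same pre-discontinuation rate, so the carry-over vanishes at the null.

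**Tipping-point scale.** A multiplier of 1.5 on method 1 corresponds to 1.5 × 0.748 = 1.12 up to 1.5 × 0.919 = 1.38 times the IGlar rate. This holds only if discontinuers ran at their arm's average. If discontinuers in both arms ran at half that rate, imputed IGlar discontinuers themselves sit at 0.63 to 0.88 of the IGlar rate. IDegLira discontinuers under method 1 are then at 0.503/0.629 = 0.80 up to 0.840/0.881 = 0.95 of those, and the same multiplier means 1.20 to 1.43. The fitted IGlar rate is therefore no clean yardstick either.

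**The case for a change.** The best case for acting is this. The protocol prints the input to method 1 but not its consequence, although 17.3.2 spells out the same consequence for the continuous endpoints. The favourable rule is the confirmatory one, no tipping point starts from method 2, and 4 to 5 points of power is not nothing when the plan has about 60%. A few explanatory sentences would cost little.

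Part of this stands. The property is real, the role reversal is unexplained, and a tipping-point multiplier has to be read against the method 1 imputation.

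The rest does not carry. The assumption appears twice in 17.4.1.1, and the contrast follows directly from it. Amendment 2 dropped the shared jump-to-reference label that once suggested parity: the continuous analyses are now called unconditional and this one method 1. Method 2 is already planned, so both results will be available, as will the analysis of the data without imputation (17.4.1.3).

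The V32A sentence covers available data. In Amendment 2 (2.21) the headings for weight, HbA1c and insulin dose name retrieved data, the hypoglycaemia heading does not, and 17.4.1.1 says that the missing period is imputed. Nobody would look for V32A episodes.

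Section 5.4 lets discontinued subjects move to any suitable marketed product, so neither method's assumption can be verified. Preferring a draw that ignores on-drug counts would be a choice among untestable assumptions.

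**Conclusion.** No change to the plan is needed. Method 1 does what the protocol says, is a valid imputation model and keeps simulated size below 2.5%. It is somewhat more favourable to IDegLira than method 2 when IDegLira truly has the lower rate: a rate ratio about 0.01 lower and power 4 to 5 points higher at 15% discontinuation, and about 0.016 to 0.022 and 6 to 9 points at 25%.

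These sizes rest on a dispersion of 2.27 to 2.74 inferred from an approximate power statement, constant rates, uniform stopping, and discontinuers typical of their arm. Added wording or a rescaled tipping-point table would alter no p-value, power or conclusion. An analyst reporting the tipping point need only remember that zero penalty is the method 1 imputation.

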17.4.1.3 Primary statistical analyses secondary estimand

Continuous endpoints body weight, HbA_{1c} and insulin dose – MMRM

This is the same analysis as for the primary objective. For insulin dose baseline HbA_{1c} will be used as covariate.

Count endpoint hypoglycaemic episodes

Here the negative binomial model described above is simply applied to data as is.

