Data on treatment-emergent hypoglycaemic episodes are presented in terms of the number of subjects with at least one event (N), the percentage of subjects with at least one event (%), the number of events (E) and the event rate per 100 years of exposure (R).

Separate summaries are made by severity considering severe or BG confirmed symptomatic hypoglycaemic episodes, severe or BG confirmed hypoglycaemic episodes, and the ADA (American Diabetes Association) classification of hypoglycaemia. The summaries are made for all and nocturnal (between 00:01 and 05.59 both inclusive) episodes respectively.

Number of nocturnal treatment-emergent severe or BG confirmed symptomatic hypoglycaemic episodes during 26 weeks will be analysed using the same J2R multiple imputation model as used for the treatment-emergent severe or BG confirmed symptomatic hypoglycaemic episodes.

| Protocol | Date: 20 November 2015 | Novo Nordisk | Version: 2.0 | Status: Final |

Page:

84 of 107

Clinical evaluation (ECG, eye examination and physical examination) change from baseline after 26 weeks

Eye examination (fundoscopy/fundusphotography) and 12-lead ECG findings will be summarised descriptively, including:

Summaries for each visit

EudraCT No.: 2015-001596-48

• Shift tables from baseline to after 26 weeks

Pulse rate change from baseline after 26 weeks

Change from baseline in pulse rate will be analysed by multiple imputation J2R.

Laboratory assessments (Biochemistry, Haematology, Calcitonin and urine analysis)

All laboratory parameters will be summarised descriptively including

- Summaries by visit
- Shift tables from baseline to after 26 weeks
- Proportion of subjects with measurements outside reference range by treatment and week
- Box plots by time since randomisation
- Listings of individual values outside reference ranges (abnormal values)

For lipase and amylase the following rule applies in the evaluation of the result:

• If the amylase or lipase baseline (at screening) value is > 3×upper normal range (UNR) the information will be regarded as medical history for that subject

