17.4.2.3 Classification of hypoglycaemia

Treatment-emergent: hypoglycaemic episodes will be defined as treatment-emergent if the onset of the episode occurs on or after the first day of trial product administration, and no later than 7 calendar days after the last day on trial product.

Nocturnal hypoglycaemic episodes: are episodes occurring between 00:01 and 05.59 both inclusive.

Hypoglycaemic episodes are classified according to the Novo Nordisk classification of hypoglycaemia (see Figure 17–1) and the ADA classification of hypoglycaemia (see Figure 17–2).

[figure not shown]
Novo Nordisk classification of hypoglycaemia

In normal physiology, symptoms of hypoglycaemia occur below a plasma glucose level of 3.1 mmol/L $(56 \text{ mg/dL})^{39}$. Therefore, Novo Nordisk has included hypoglycaemia with plasma glucose levels below this cut-off point in the definition of BG confirmed hypoglycaemia.

Protocol	CONFIDENTIAL	Date:	20 November 2015	Novo Nordisk
Trial ID: NN9068-4229		Version:	2.0	
UTN: U1111-1168-9343		Status:	Final	
EudraCT No.: 2015-001596-48		Page:	85 of 107	

Novo Nordisk uses the following classification (see Figure 17–1) in addition to the ADA classification:

- Severe hypoglycaemia according to the ADA classification
- Symptomatic BG confirmed hypoglycaemia: An episode that is BG confirmed by plasma glucose value <3.1 mmol/L (56 mg/dL) with symptoms consistent with hypoglycaemia
- Severe or BG confirmed symptomatic hypoglycaemia: An episode that is severe according to the ADA classification²⁴ or BG confirmed by a plasma glucose value <3.1 mmol/L (56 mg/dL) with symptoms consistent with hypoglycaemia

Note: Glucose measurements are performed with capillary blood calibrated to plasma equivalent glucose values

Figure 17–1 Novo Nordisk classification of hypoglycaemia

[figure not shown]
20 November 2015 Novo Nordisk Protocol Date: Trial ID: NN9068-4229 Version: 2.0 CONFIDENTIAL UTN: U1111-1168-9343 Final Status: 86 of 107

Page:

ADA classification $\frac{24}{2}$ of hypoglycaemia

EudraCT No.: 2015-001596-48

- Severe hypoglycaemia: An episode requiring assistance of another person to actively administer carbohydrate, glucagon, or take other corrective actions. Plasma glucose concentrations may not be available during an event, but neurological recovery following the return of plasma glucose to normal is considered sufficient evidence that the event was induced by a low plasma glucose concentration

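### Does the confirmatory hypoglycaemia model divide at least 27 weeks of completed counts by a shorter observed time?

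*Protocol*

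**What the plan says.** The hypoglycaemia comparison is the second test in the hierarchy of protocol section 17.4.1, and section 17.4.1.1 gives its analysis. For subjects who stop trial product early, events are imputed over the span "time of premature discontinuation to planned TE period [max of 27 weeks and longest TE exposure time observed in the trial", using IGlar rates. Step 1 fits a Bayesian negative binomial model to the event data and step 2 draws the missing counts. In step 3, "for each of the complete data sets, the number of events is analysed using a negative binomial model". One sentence then sets the offset for the model: "the logarithm of the time period, in which a hypoglycaemic episode is considered treatment-emergent, will be used as offset".

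Four other places bear on the reading:

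- Section 17.4.2.3 counts an episode as treatment-emergent if it starts "no later than 7 calendar days after the last day on trial product".
- Section 17.4.1.3, for the secondary estimand, says: "Here the negative binomial model described above is simply applied to data as is".
- Within 17.4.1.1, the rate ratio is introduced as a ratio of the "rate of treatment-emergent severe or BG confirmed symptomatic hypoglycaemic episodes during 26 weeks". The rule for declaring superiority glosses it as the "rate ratio of rate of treatment-emergent severe or BG confirmed symptomatic hypoglycaemic episodes during-treatment".
- Section 17.4.2.2 carries the same model over to nocturnal episodes.

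Amendment 2 (its section 2.21) renames the approach method 1 and leaves the offset sentence alone.

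**The concern.** Only one definition of treatment-emergent hypoglycaemia appears in the protocol, and it stops a week after the last dose. If that definition is put straight into the offset sentence, the numerator and denominator of a discontinued subject's rate cover different spans: events to at least 27 weeks, time only to last dose plus 7 days.

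No later data could close the gap. Section 8.5.2 collects episodes only up to V33, and the contacts listed in 8.1.7 after that do not ask about them. Section 6.1 expects 354 of 416 subjects to complete on product, so 416 − 354 = 62 subjects could be affected.

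The test also gates HbA1c superiority and insulin dose. If the mismatch were real, unequal stopping between arms would bias the rate ratio, and equal stopping would inflate its standard error. The two descriptions of the rate ratio, and the reuse of the same model on unimputed data, add to the impression that the period was never settled.

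**Working it through.** **1. The plan's own power figure.** Section 17.1 gives power in the order of 60% for 1.8 events per patient-year and a rate ratio of 0.66, with 208 per arm. It does not state the dispersion k or which arm has the 1.8. Take 1.8 as the IGlar rate and t = 0.5 year:

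Var(log RR) = [1/(1.8 × 0.5) + 1/(1.8 × 0.66 × 0.5) + 2k]/208 = [1.111 + 1.684 + 2k]/208

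With k = 0 (Poisson) the power is 95%, so the 60% implies overdispersion. Solving for 60% gives k = 2.27: variance (2.795 + 4.54)/208 = 0.0353, SE 0.188, and 0.4155/0.188 − 1.96 = 0.25, that is, 60%. If 1.8 is the IDegLira rate, k = 2.74. Either value is an assumption.

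**2. What the mismatch would do to one subject.** Observed treatment-emergent time is the stopping week plus 1.

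- Stop at week 5: 27/6 = 4.5-fold.
- Stop at week 13: 27/14 = 1.9-fold.
- Stop at week 20: 27/21 = 1.3-fold.

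**3. What it would do to the test.** Method 1 was simulated with an IGlar rate of 1.8, k = 2.27, stopping uniform over 26 weeks unless stated, a 27-week horizon, 3000 trials and 20 imputations. Matched means offset log(27 weeks). Mismatched means offset log(observed treatment-emergent time).

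| True RR | Stopping (IDegLira / IGlar) | Matched | Mismatched |
|---|---|---|---|
| 0.66 | 15% / 15% | RR 0.672, power 54% | RR 0.674, power 44% |
| 0.66 | 15% / 15%, all in weeks 13–26 | power 58% | power 56% |
| 0.66 | 15% / 15%, all in weeks 0–13 | power 49% | power 30% |
| 0.66 | 20% / 10% | RR 0.68, power 52% | RR 0.755, power 22% |
| 1 | 15% / 15% | error 1.9% | error 1.1% |
| 1 | 10% / 20% | RR 1.00, error 2.4% | RR 0.91, error 6.1% |

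A separately coded, smaller simulation (280 trials, 10 imputations, k = 2.3) agrees within its error of about 3 points on power and 1–2 points on null rejection rates. At RR 0.66 it gives 58% against 48% for 15%/15% and 49% against 20% for 20%/10%. Under the null with 10%/20% the error is 1.4% against 5.7%. A mismatched offset would therefore matter.

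**4. Does the text specify it?** Set the passages side by side.

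- The horizon in 17.4.1.1 is itself described as a treatment-emergent period, the planned one. Its floor of 27 weeks is 26 weeks of treatment plus the 7 days of 17.4.2.3.
- The offset in the same section is the length of the treatment-emergent period. In a data set completed to the planned treatment-emergent period, that period is the length in question.
- In the data of 17.4.1.3, nothing has been imputed and the treatment-emergent period is the observed one. A single offset sentence thus serves both data sets, taking its value from the data set being analysed. The same holds for step 1, which is fitted before imputation.
- The estimated quantity is a ratio of rates. Events over 27 weeks divided by 6 weeks is not a rate over any period, so the mismatched reading contradicts the definition in the same section.
- Only discontinued subjects' counts are extended. Completers keep their own treatment-emergent time of about 27 weeks under either reading.

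**The case for a change.** The strongest case for a change is that the protocol chose to fix the offset for a confirmatory test, in words that its only definition ties to last dose plus 7 days. No sentence connects the planned period to the offset. Amendment 2 revisited this analysis without making the connection. In an open-label trial, two readings that reach different decisions in 12.5% of simulated trials (equal 15% stopping, RR 0.66) should not be left open, and one sentence would close them.

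Part of this stands. The link is implied and not written, and calling the rate ratio a during-treatment quantity in the decision rule is loose next to the 26-week definition. That phrase is a gloss on a quantity already defined, matches no separate endpoint in section 4.2.2.1, and does not mention the offset.

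The rest carries less weight. The 12.5% compares a coherent analysis with one that no analyst would choose once the two time spans are written out. The error inflation needs IGlar subjects to stop twice as often as IDegLira subjects, and nothing in the protocol suggests that. Its only directional hint, the gastrointestinal events named for IDegLira in 18.1.1.1, points the other way, where the mismatch would be conservative. How analysis time is built in an imputed data set is commonly left to the statistical analysis plan, which is not at hand.

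The obvious one-line patch also has its own trap. Imputation starts at discontinuation while the observed window runs 7 days further. An offset of observed plus imputed time would therefore give a week-5 stopper 6 + 22 = 28 weeks unless the start of imputation were moved too. That overlap and the data-dependent horizon each change RR by about 0.01 or less.

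**Conclusion.** No change follows. The natural reading of section 17.4.1.1 is the matched one: the planned treatment-emergent period for discontinued subjects with imputed counts, each completer's own treatment-emergent time, and observed time in step 1 and in 17.4.1.3. On that reading the estimate is sound, with simulated power of about 54% to 58% at 15% stopping per arm, close to the stated figure, and one-sided error at or below 2.5% in the cases run.

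The losses of 2 to 19 points of power under equal stopping, and the 6.1% error under 10%/20% stopping, belong to a reading that conflicts with the section's own definition of the rate ratio. They also depend on dispersion, stopping times and an arm split that the protocol does not give. What remains is an unwritten detail and a loose phrase, both of which analysts would resolve the same way. Recording the step-3 offset in the analysis plan would be tidy, but the protocol does not depend on it.
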